16.4 Lung transplantation procedure (usual care/comparator)

Participants randomised to receive lung transplant only will undergo transplantation by a transplant surgical team in line with routine clinical practice and will be followed up by current standard of care.

16.5 Lung transplantation with skin sentinel flap transplant (intervention)

Participants randomised to receive lung transplantation with an additional SSF transplant will receive a SSF from the same donor as the lung, at the same time as the lung transplant. The SSF (10cm x 3cm) will be anastamosed onto the ulnar artery of the recipient's non-dominant forearm at the same time as lung transplantation. The two procedures will be performed simultaneously to ensure that total operative and anaesthetic time is not prolonged. The arm will be abducted away from the body onto an arm table or anaesthetic arm board, to avoid interference with the lung transplant team. Inset of the forearm skin

flap takes 1-2 hours. Lung transplantation takes an average of 4-12 hours, depending on the complexity of the procedure.

In the unlikely event that there is an anatomical or personal reason that a SSF cannot be anastomosed onto the non-dominant forearm, then it can be implanted onto their dominant forearm. Alternatively, another site, such as the groin or axilla can be chosen, or the participant can be withdrawn from the study. The options will be described within the patient information sheet and discussed and confirmed with the patient pre-operatively.

16.6 Retrieval of the lung

Retrieval of the lung will be performed according to current practice as directed by NHSBT by the National Organ Retrieval Teams. Organ donation is coordinated by the NHSBT. The specialist nurses (SNs) discuss organ donation with the families and seek consent for donation. Some families refuse any donation. Some refuse donation of a skin flap but permit lung donation. Despite consent being obtained for organ donation, not all patients proceed to donation. This commonly in the case of donation after circulatory death (DCD) as compared to donation after brainstem death (DBD) where the logistics are more predictable.

16.7 Sentinel skin flap retrieval

If a suitable donor, with consent obtained for both lung and skin donation is matched with a patient, their local participating site will be informed (in accordance with NHSBT procedures). The dedicated retrieval team will be contacted by the participating site to ensure availability for skin retrieval, as there may be situations where transplantation procedures are already underway elsewhere and retrieval of the skin flap is not possible. If the patient confirms their consent to take part in the study, they will be randomised. If they are randomised to receive a SSF, the dedicated retrieval team will be placed on standby to travel to the donor hospital to retrieve the SSF alongside the usual lung retrieval team.

If skin flap retrieval is not possible or viable then lung retrieval and transplantation will proceed as planned without skin flap transplantation.

Where a skin flap is retrieved and not transplanted, the NHSBT will be informed and the skin flap will be discarded or used in other research approved by NHSBT provided the family has consented for such use. The study database will record that the skin flap was retrieved and not used. Skin flaps not used for the purpose of this study will be tracked and documented within NHSBT systems to ensure that they are handled and managed appropriately and in accordance with relevant approvals.

In the unlikely event that two donations are approved at the same time, and the skin flap retrieval team are not available to retrieve both SSFs, then the donation logistically/geographically nearest to the retrieval team would take priority; and only that recipient randomised. If that recipient randomises to lung only then the second recipient may be randomised.

Rarely, a skin flap may be required for both a lung transplant, as part of this study, and a intestinal transplant, as part of another study. In this instance, the SSF will be split in two for each recipient or prioritised for the intestinal transplant.

16.8 Detecting, diagnosing and managing rejection

If any events occur that suggest lung transplant rejection, such as a clinically significant drop in forced expiratory volume in 1 second (FEV1) of >10% or new symptoms of lung failure, then the usual sequence of clinical investigations will be performed and may include a tissue biopsy. The decision to perform a biopsy will be made in accordance with local site practice.

If a lung biopsy is performed, a skin biopsy will also be taken by the local health team for any participants with a SSF. The biopsy samples taken (lung and/or skin) will be examined by the local pathology team. Remaining samples embedded in paraffin blocks will be sent to the University of Oxford for the mechanistic studies at the completion of the 12 month follow up period;

If signs of skin rejection occur, the participant will either be examined in person by a study clinician (e.g. during a routine or extra visit) or they will be asked to send a photo of their skin flap to the research team/local healthcare transplant teams. The sending of any photographs from a participant to the research team or between local healthcare team and the research team will be done in accordance with local site practice for remote consultations; photographs will be stored within the participant's medical notes.

Consensus determination of rejection change in the skin will trigger an outpatient visit. Clinical features of the rash, investigations such as blood tests, sputum or bronchial brushings/, bronchoalveolar lavage if available, and lung function assessment and skin and/or lung biopsies (if taken) will be analysed for rejection.

All investigations for rejection will be performed at the discretion of the participating site/clinician and considered part of standard of care. This does not include the protocol skin biopsies taken at 3, 6 and 12 months which are required for the purpose of the study only.

A summary of the biopsy requirements for suspected rejection is provided in Table 2.

Table 2: Biopsy requirements/investigations for suspected rejection events

	Lung biopsy	Skin biopsy required (sentinel skin flap recipients only)
Signs/symptoms of lung rejection WITHOUT visible skin changes/rash only	In accordance with local policy*	Yes
Signs/symptoms of lung rejection WITH visible skin changes/rash only	In accordance with local policy*	Yes
Visible skin changes/rash	In accordance with local policy if signs of lung rejection present	Yes

*Where it is local policy to biopsy the lung, the date and result of the biopsy will be recorded on the case report form, and some of the biopsy sample will be stored for later mechanistic analysis

16.9 Monitoring the sentinel skin flap

For participants randomised to the intervention, both participants and healthcare staff will be taught by the research team how to monitor the skin for signs of rejection. The skin will be monitored daily by the participant for visible signs of rejection, such as erythema or rash. Participants that experience a skin rash may be asked to take a photograph of their skin rash to send to their local research team prior to being asked to return to the site for any investigations.

Any photos sent to the local research team will be done so in accordance with the local Trust's policies on remote consultations and any approved NHS systems. The images will not be stored within the study database.

Whilst site staff will receive full training on the study, many will have limited or no experience in SSF transplantation. They can seek further assurance regarding the assessment of the skin for signs of rejection from the Chief Investigator or designated point of contact. Where this is required, the local study team may send a photograph of the skin flap to the Chief Investigator for review using secure nhs.net e-mail. Images will not identify the participant and will be transferred in accordance with applicable site policies. A consensus will be made between the Chief Investigator and local site clinician.

16.10 Treatment of rejection

Acute rejection of the lung will be detected and treated according to established practice at the participating transplant centre. If rejection in either skin or lung is confirmed by clinical findings or pathology (BANFF grade>1 skin and ISHLT grade A>1 for lung) this will be recorded. Decision on instituting treatment will be at the discretion of the local care team. Treatment given, treatment date and outcome of treatment for rejection will be recorded. Normal local transplant follow-up protocols will continue with the addition that the skin flap will also be biopsied whenever the lung is biopsied.

The usual treatment of biopsy proven acute rejection of the SSF for Banff Grade 1 rejection will be a single 500mg dose of intravenous methylprednisolone with correction or escalation of daily immunosuppression if required, and for Banff Grade 2-4 rejection, is 3 daily doses of 500mg intravenous methylprednisolone with escalation of daily immunosuppression if required. However, any such treatment is at the determination of the clinical relevance by the local transplant team.

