6 TRIAL SYNOPSIS

Full Trial Title:	rial Title: Efficacy and mechanism of sentinel skin flap reduction of solid		
	organ (lung) transplant rejection: A randomised controlled trial		
Short Title:	Sentinel Skin flap in Lung Transplant RCT		
Trial Acronym:	SENTINEL		
Trial Design:	SENTINEL is a multicentre, paralle open-label RCT.	I group, two-arm, superiority,	
Trial Participants/Target Population:	Adults (aged 18 years or over) on the waiting list to receive a lung transplant (single or bilateral and including those in combination with other organs) where offered a simulatnaeous lung and skin transplant		
Eligibility criteria:	Inclusion: 1. Intended recipient of a lung transplant 2. Aged 18 years or over 3. Capable of giving informed consent Exclusion: 1. Any significant disease or disorder which, in the opinion of the Investigator, may either put the participants at risk because of		
	participation in the study, or may influence the result of the study, or the participant's ability to comply with study procedures 2. Severe peripheral vascular disease with no vessels available for inset of the skin flap		
No. of trial arms 2			
Intervention Lung transplant with sentinel skin flap transplant		flap transplant	
Comparator Lung transplant			
Planned Sample 152 participants (76 per trial arm) Size:			
Planned Recruitment Period	36 months		
Target no. of centres:	5 NHS cardiothoracic transplant centres in the UK		
Follow-up duration:	Each participant will be followed-up for 12 months from the point of transplantation.		
	Objective	Outcome Measure	
Primary objective	To assess the efficacy of the	Lung rejection events in the first	
and outcome	sentinel skin flap (SSF) at	12 months, defined by clinical	
measure	reducing rates of acute lung	criteria diagnosis and/or biopsy	
	rejection by 12 months post- transplantation	diagnosis of rejection (ISHLT grade A≥1 for lung)	
		 TCOME MEASURES section of the ives and outcome measures.	

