9.3 Secondary objectives and outcome measures

	Objective	Outcome measure	Time point(s) of	Data required	Source data
			evaluation of this		(including location)
			outcome measure		
			(if applicable)		
1.	To compare the	Diagnostic accuracy	Up to 12 months post	Date of first diagnosed	Histology reports
	diagnostic accuracy	(sensitivity,	randomisation	lung rejection; date and	(skin and lung
	of the sentinel skin	specificity, negative		method of first	biopsies)
	flap to the current	predictive value and		diagnosed skin	Participant's medical
	reference standard	positive predictive		rejection.	notes
	(organ biopsy	value) of the sentinel			
	and/or clinical	skin flap compared			
	diagnosis) ²	to current reference			
		standard (biopsy			
		and/or clinical			
		diagnosis) ²			
2.	Safety of sentinel	a. Number and	Up to 12 months post	Date of randomisation;	Participant's medical
	skin flap	severity of skin flap	randomisation	date of first diagnosis of	notes and
	transplantation ²	rejection episodes		skin rejection; date of	

SENTINEL_Protocol_V1.1_27Apr2023.docx IRAS number: 318347 REC Reference: 23/LO/0248

		T	T	1	Ι .
		(defined by biopsy		death (if prior to	Histology reports
		BANFF grade ≥ 1) and		diagnosis of skin	(skin biopsies)
		time to firstrejection		rejection); date of	
		diagnosis ²		withdrawal (if prior to	
				diagnosis of skin	
				rejection); severity of	
				rejection (BANFF grade).	
		b. Transplanted lung	Up to 12 months post	Date of randomisation;	Participant's medical
			randomisation	date of first loss of lung	notes/death record
		'		failure; date of death;	,
				date of withdrawal (if	
				prior to lung loss or	
				death)	
		c. Transplant lung	12 months post	Lung function tests	Participant's medical
		function ¹	randomisation	(spirometry): Vital	notes
				capacity (absolute	liotes
				values and % predicted);	
				Forced expiratory	
				volume (absolute values	
		1.6	11. 1. 42	and % predicted)	De distance de la constance de
		d. Surgical	Up to 12 months post	Surgical complications	Participant's medical
		complications and	randomisation	(flap failure, wound	notes
		complications		healing problems,	
		relating to the SSF		infection, skin necrosis,	
		(such as infection,		nerve injury);	
		skin loss, nerve		Delayed complications	
		injury) ¹		(pain, hand symptoms	
				including paraesthesia,	
				numbness, weakness)	
		e. Development of	Events up to 12	Presence of de-novo	Immunological
		de-novo donor	months post	antibodies	laboratory report

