24.2 Sample Size/Power calculations

The anticipated 12-month rejection rates for lungs in the control arm by 12 months is 80%. Published rates vary between 33-100% (43–46) depending on definition and grade of rejection and method of analysis. However, a comprehensive study of regular transbronchial biopsies in 299 lung transplant patients showed a cumulative incidence of rejection (≥grade A1) of 91.7% in the first 12 months and (≥grade A2) of 77.9% (46).

In the SSF intestinal study, we observed a 72% reduction in biopsy-proven acute rejections from the 77% rejection rate in the control arm reducing to 22% in the with skin arm. However, as a more conservative estimate for this study, we consider a relative reduction of a third from 80% to 53.33% (corresponding to an absolute difference of 26.67%) to be clinically meaningful. 128 participants who have had a transplant are required for the analysis to achieve 90% power at a two-sided significance level of 5%. To allow for a 15% loss to follow-up or death by 12 months (76 per trial arm) 152 participants need to have been randomised and transplanted. In total, approximately 254 randomisations will be required to achieve this number and account for participants not proceeding with transplant.

Assessment of the diagnostic accuracy of the SSF compared to the current reference standard (organ biopsy) is a secondary objective of this study, and is undertaken in participants who received an SSF. Assuming approximately 80% specificity, and 90% specificity, based on previous studies, 95% confidence intervals (Wilson method) around the sensitivity, specificity, positive and negative predicted values will have a width of approximately 20-30%, depending on the observed sensitivity, specificity and event rates. A sample size of 64 participants receiving SSF and providing one-year follow-up data, an expected rejection rate of 53%, and anticipated values of 80% and 90% for sensitivity and specificity, respectively, will provide approximately 80% power (at a one-sided 5% significance level) to show that the observed sensitivity and specificity in the study are statistically significantly higher than 60% and 70%, respectively.

Since the proposed mechanistic sub-studies are intended to be hypothesis generating, no formal sample size calculations have been performed.

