24.5 Primary outcome

The primary outcome of the study is absolute difference in rejection rates (clinical or biopsy) at 12 months post randomisation. The absolute risk difference, and corresponding 95% CIs, will be obtained from a mixed-effects Cox proportional hazards models, including treatment and adjusted for centre as a random effect, analysing time to first lung rejection (43). If the proportional hazards assumption is not met, alternative parametric methods will be considered. The treatment groups will also be compared using Kaplan-Meier curves and log rank tests. Events, by severity, will be summarised descriptively. Sensitivity analyses for the primary outcome will include alternative definitions of the primary endpoint, including lung rejections of ISHLT grade 2 or higher, and ISHLT grade 3 or higher. The primary analysis will

be repeated for the per-protocol population, excluding participants with major deviations from the study protocol.

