24.8 Additional analyses

A supplementary analysis, using the approaches for the primary outcome, will be run using a composite outcome of rejection free survival, whereby lung rejection (ISHLT A grade 1 or higher), graft failures (biopsy BANFF grade \geq 1) and death are counted as events. As participants can have recurrent lung or skin rejection events, an exploratory analysis of the ordered multiple events will be undertaken using the Prentice, Williams and Peterson total time models (44). Visual representation of recurring events will also be presented.

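### Section 16.10 sets the recording threshold for biopsy-confirmed rejection one grade above the endpoints, so sites may differ on whether a grade 1 biopsy is a dated rejection event

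*Protocol*

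**What the plan says.** Section 16.10 (Treatment of rejection) states when a confirmed rejection is to be recorded: if it is "confirmed by clinical findings or pathology (BANFF grade>1 skin and ISHLT grade A>1 for lung) this will be recorded". The clinical route carries no grade limit. The pathology route is limited to grades above 1.

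The endpoints use a lower threshold:
- Section 6 (synopsis), primary outcome: a clinical diagnosis and/or a biopsy "diagnosis of rejection (ISHLT grade A≥1 for lung".
- Section 9.3, secondary outcome 2a (skin flap rejection): "BANFF grade ≥ 1) and" time to first diagnosis.
- Section 24.8, supplementary composite: "lung rejection (ISHLT A grade 1 or higher", with Banff grade 1 or above for the graft-failure component.

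Section 24.5 uses "lung rejections of ISHLT grade 2 or higher" only as an alternative definition in a sensitivity analysis.

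The paragraph of section 16.10 that follows the recording rule begins "The usual treatment of biopsy proven acute rejection of the SSF for Banff Grade 1 rejection", so the section itself regards Banff Grade 1 as rejection.

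**The concern.** The primary analysis is time to first lung rejection (section 24.5), built from the date of first diagnosed lung rejection (section 9.2). Whether a patient has an event, and when, depends on what a site declares to be a rejection. A site that follows section 16.10 to the letter would declare no event for an asymptomatic A1 biopsy, or would date the event later if A2 followed. A site that follows the synopsis would declare and date it at once.

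Three features of the design make such a difference hard to detect or correct:
- There is no central review of rejection (section 10.6).
- Centres already differ in how they assess rejection, which is the stated reason for stratifying by centre (section 15.4). Stratification and a random centre effect allow for different event rates; they do not make the definition of the event the same.
- Rejection is kept out of SAE reporting (section 20), so that route offers no cross-check.

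Site staff also know the allocation (section 15.7), and visible flap changes prompt extra investigation in one arm only (section 16.8). An ambiguous grade 1 rule could therefore be applied differently between arms. The protocol gives no basis for predicting the direction.

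**Working it through.** **Step 1. The thresholds side by side.** Grades are whole numbers, so >1 means 2 or higher.

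| Place in protocol | Purpose | Lung | Skin |
|---|---|---|---|
| 16.10, first paragraph | recording a pathology-confirmed rejection | A2 and above | Banff 2 and above |
| 16.10, second paragraph | describing biopsy-proven flap rejection | – | Banff 1 and above |
| 6, synopsis | primary outcome | A1 and above | – |
| 9.3, outcome 2a | skin rejection | – | Banff 1 and above |
| 24.8 | composite | A1 and above | Banff 1 and above |
| 24.5 | sensitivity analyses | A2 and above; A3 and above | – |

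The recording rule is exactly one grade stricter than each endpoint that it serves. For lung it coincides with a sensitivity definition, not with the primary one.

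**Step 2. What reaches the database by other routes.** The footnote to Table 2 (section 16.8) puts lung biopsy dates and results on the CRF where biopsy is local policy. Section 17.3 collects biopsies and their results when a rejection event is detected, and biopsy-proven or clinical rejection at 3, 6 and 12 months. Section 18.2 has locally reported lung and skin histology entered in the database. None of these carries a grade limit. The histology is therefore not lost. What remains open is whether a grade 1 result is declared as a rejection event, with the method, reason for suspicion, treatment and resolution date that section 17.3 attaches to one.

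**Step 3. Size in the protocol's cited series.** Section 24.2 cites a "cumulative incidence of rejection (≥grade A1) of 91.7% in the first 12 months and (≥grade A2) of 77.9" per cent.
- Patients with A1 but nothing higher: 91.7 − 77.9 = 13.8 percentage points.
- Share of patients with any event of A1 or above: 13.8 / 91.7 = 15.0%.
- Applied to a control arm: 0.138 × 64 = 8.8, about 9 analysed patients; 0.138 × 76 = 10.5 of those randomised and transplanted.

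**Step 4. The plan's own sample size, then an illustration.** Inputs from section 24.2: 80% v 53.33%, 90% power, two-sided 5%, 15% loss. With pooled variance and no continuity correction:

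n per arm = [1.960 × √(2 × 0.6667 × 0.3333) + 1.2816 × √(0.80 × 0.20 + 0.5333 × 0.4667)]² / 0.2667² = (1.3066 + 0.8195)² / 0.07111 = 63.6, rounded up to 64.

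That gives 128 in total, and 64 / 0.85 = 75.3, rounded up to 76 per arm, or 152. The stated figures reproduce.

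Suppose the same share of events went undeclared in both arms. This is an assumption; the protocol gives no such figure. With 64 per arm and the same two-proportion formula:

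| Share undeclared | Rates compared | Power |
|---|---|---|
| 0% | 80.0% v 53.3% | 90% |
| 5% | 76.0% v 50.7% | 85% |
| 10% | 72.0% v 48.0% | 80% |
| 15% | 68.0% v 45.3% | 74% |
| 20% | 64.0% v 42.7% | 68% |

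Unequal loss between arms would bias the comparison as well as cost power.

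**The case against.** The best reply is that section 16.10 is not where the data-collection rules sit. It concerns treatment. Sections 16.8, 17.3 and 18.2 send biopsy results to the CRF or database at every grade, section 9.2 names the histology report as a source for the primary outcome, and clinically confirmed rejection is recorded without a grade limit. A statistician could derive the first A1-or-above date from the dated results. This stands, and it limits the consequence. A reader might infer from section 16.10 alone that patients with only A1 disease would have no histological record; the protocol does not support that. It does not remove the conflict, because the protocol does not say whether the declared event or the biopsy result defines the endpoint when the two disagree.

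The sign may also be a slip. The second paragraph of section 16.10 makes a cut-off that excludes grade 1 hard to believe as intended, and a dropped underline turning ≥ into > cannot be ruled out. Against that, ≥ appears intact in sections 6, 9.3 and 24.2, and both thresholds in section 16.10 read >.

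The 13.8 points do not carry over directly. The cited series used regular transbronchial biopsies, whereas here only some centres do surveillance biopsies (section 8.1), biopsy follows local practice (section 16.8), and clinical diagnosis also counts. This stands too.

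**Conclusion.** The protocol is inconsistent as written: for biopsy-confirmed rejection, the recording threshold in section 16.10 is one grade above the primary outcome, secondary outcome 2a and the composite, and it conflicts with its own next paragraph. The supported consequence is that some sites may not declare and date grade 1 biopsies as rejection events, so that first-event status and date vary by centre. This is a possibility, not a certainty.

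The 13.8 points (15% of patients with any A1-or-above event) are an upper-range illustration. They would apply only if biopsy intensity matched the cited series, every A1-only patient went undeclared, and no clinical diagnosis was made instead. The power figures rest on equal loss in both arms and are illustrative in the same way.

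Two further inferences are tempting and should not be drawn. One is that the planned 80% control rate is really an A2-or-above rate because it lies near 77.9%. Section 24.2 does not tie the 80% to a grade and gives a published range of 33–100%; with less frequent biopsy, an A1-or-above rate below 91.7% is plausible. The other is that the grade 2 and grade 3 sensitivity analyses lose their meaning. They need no A1 events and can be computed under either reading. The sample size of 128, inflated to 152, is unaffected.

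**What to change.** First check the sign in the approved protocol. If it reads >, amend the recording sentence in section 16.10 to the endpoint grades, lung ISHLT A≥1 and skin Banff ≥1, and use the same thresholds on the rejection-event CRF, which is not among the documents. Record the grade for each event, so that the primary and the grade 2 and grade 3 sensitivity definitions all come from one record. Leave the treatment text in section 16.10 untouched; the change concerns recording only.

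The cost is a wording amendment and a CRF label or field. It needs no extra patients, visits or biopsies. Correcting inconsistently declared events after follow-up would be harder.
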